Prevalence of Thiamine Deficiency in Hospitalized Non-Alcoholic Veterans

NCT05480943

July 29, 2025

Protocol – Biomedical

1867369 [name], PhD

Title: Prevalence of Thiamine Deficiency in Hospitalized Non-Alcoholic Veterans

Principal Investigator: [name], MD, PhD

Abbreviations:

ADL's	Activities of Daily Living
AIC	Acute Inflammatory Condition
CIC	Chronic Inflammatory Condition
COVID-19	Coronavirus Disease 2019
GI	Gastrointestinal
hs-CRP	Highly Sensitive C-reactive Protein
IADL's	Instrumental Activities of Daily Living
IV	Intravenous
MoCA	Montreal Cognitive Assessment
TD	Thiamine Deficiency
TDD's	Thiamine Deficiency Disorders
ThDP	Thiamine Diphosphate
WE	Wernicke's Encephalopathy

Revisions History: 8

Table of Contents:

Background:	3
Study Aims/Objectives:	5
Study Population:.....	5
Vulnerable Populations:	6

Sample Size:	6
Recruitment Process:	6
Screening Procedures:	7
Informed Consent Process:	7
Data Collection Procedures:	7
Study Duration/ Study Timeline:	9
Study Endpoints	9
Study Locations:	9
International Research:	9
Participant Compensation:	10
Economic Burden to Participants:	10
Risk to Participants:	10
Benefits to Participants:	10
Privacy of Participants:	11
Data Management and Confidentiality:	11
Provisions to Monitor the Data to Ensure the Safety of Participants	11
Data and Specimen Banking	12
Sharing of Results with Participants	12
Withdrawal of Participants	12
Approach to Analysis:	12
Resources Available.....	14
Mentorship Plan for Medical Trainees Conducting Research	14
References:	14

Background:

Thiamine deficiency (TD) causes a variety of thiamine deficiency disorders (TDDs) such as neuropsychiatric disturbances, polyneuropathy, ataxia, weakness and falling, and non-ischemic heart failure. Left untreated, TD can be associated with poor quality of life, loss of independence, and inability to complete activities of daily living. The prevalence of TD in non-alcohol using hospitalized Veterans is not known but is probably much higher than the general population which is thought to be less than 3%. Loss of functional ability leads to increased need for rehabilitation and consequent cost of healthcare. The objective of this proposal is to measure the prevalence of TDDs in Veterans who do not use excess alcohol who are ill enough to require hospitalization, determine if inflammation increases the risk of developing TD, and determine the optimal cutoff points for two biomarkers of TD to diagnose of TDDs.

The body's supply of thiamine depends entirely on dietary intake, there is no endogenous synthesis^{1,2}. Thiamine is an essential cofactor for the metabolism of carbohydrates and amino acids^{1,2}. Thiamine deficiency (TD) can develop quickly, within 18 days on a thiamine deficient diet or within 72 hours in critically ill patients³. Hospital inpatients are more likely to have micronutrient deficiencies⁴. COVID-19 infections may particularly increase the risk of TD because appetite, taste

and smell can be adversely affected. Neurologic complications in patients with COVID-19 are common in those requiring hospitalization⁵, and thiamine responsive COVID-19 related encephalopathy has been described⁶. Thiamine deficiency disorders (TDDs) include conditions such as neuropsychiatric disturbances, polyneuropathy, ataxia, nausea and vomiting, weakness and falling, and non-ischemic heart failure.

TDDs are more common than currently appreciated in patients with specific medical conditions which often lead to hospitalization and subsequent rehabilitation needs. While TD and TDDs are reportedly less than 3% in high-income countries, there is a lack of generalizable prevalence, particularly in vulnerable populations such as the economically challenged, elderly, and chronically ill. Because symptoms of TDDs are often vague (fatigue, leg edema, imbalance, confusion, mood disorders, gastrointestinal (GI) upset, or muscle weakness) they are frequently attributed to comorbid diagnoses so under diagnosis among non-alcoholics is common⁷. Despite many published accounts of TD in acutely and chronically ill patients with conditions such as end stage renal disease⁸, cancer⁹, heart failure^{10,11}, dementia¹², acute psychiatric illness¹³, stroke¹⁴, diabetic ketoacidosis¹⁵, critical illness¹⁶, severe COVID-19 infections⁶, and medically complicated obesity^{17,18}, there is a lack of appreciation for TDD diagnosis broadly, and specifically in Veterans. Acute illnesses which increase metabolic demands can lead to TD more quickly including severe sepsis^{3,16}. Elderly patients admitted to hospital seem particularly vulnerable¹⁹⁻²¹. Those who develop TDDs because of illness that leads to hospitalization will have more rehabilitation needs at discharge²². If TD is left untreated, the rehabilitation efforts will be less successful. If hospital providers were cognizant of increased risk of TDDs in their patients, it is more likely that thiamine replacement would occur leading to the best possible outcomes for patients and health systems alike. Based on a review of published accounts of TD in specific illness states, we estimate the prevalence in hospitalized patients could be as high as 25%^{12,14,20,21,23-27}. The lack of basic prevalence data is an important knowledge gap that, left unanswered, will perpetuate the current state of under-diagnosis and under-treatment leading to persistent loss of function among at-risk Veterans.

We hypothesize that TD and TDDs are not rare in hospitalized Veterans who generally have higher chronic disease burden²⁸ and an incidence of malnutrition of 24% or more²⁹⁻³¹. The etiologies of TD can be broadly categorized as insufficient intake (including malabsorption and toxin interference), increased need due to inflammatory stress (e.g. sepsis or active malignancy), and increased losses such as vomiting, diarrhea, dialysis⁸, or chronic diuretic use¹⁰. Hospitalized patients often have increased inflammatory stress due to acute and chronic forms of inflammation with concomitant cachexia^{32,33}. Many use diuretics for hypertension and heart failure treatment. Most Veterans have poor intake leading up to admission from anorexia induced by acute and chronic illness and many suffer poverty and food insecurity with resultant malnutrition and micronutrient deficiencies³¹.

TDDs often mimic other diseases and symptoms overlap with acute medical illnesses leading to missed opportunities for diagnosis and treatment. Many practitioners are unaware that TD occurs in non-alcohol using adults and the literature is full of case reports of near-miss diagnoses including mimics of Guillain-Barre syndrome^{34,35}, non-ischemic cardiomyopathy^{36,37}, refractory shock³⁸, worsening dementia²⁶, seizures³⁹, and acute psychosis⁴⁰. In a stroke population admitted to acute inpatient rehabilitation, there was a 14% prevalence of TD with low plasma thiamine levels and an additional 49% with “low normal” levels, with over half of patients afflicted¹⁴. Thiamine is critical for brain function and as such, recovery from a stroke or other neurological insult requires at least adequate thiamine stores and perhaps higher than usual levels to meet rehabilitation goals. It is possible that acute illnesses resulting in prolonged debility requiring rehabilitation are in part due to TD, and that administration of thiamine may improve outcomes.

Case definitions of TDDs and evaluation of appropriate cutoff points of biomarkers are lacking. Many authors point out that the diagnosis of TD is a clinical one, not based on blood levels, although low blood levels are confirmatory^{14,17,18}. TD should be defined as individuals with consistent clinical

symptoms AND either a low thiamine biomarker or significant improvement in or resolution of symptoms of TD after receiving thiamine supplementation^{1,17,18}. Unfortunately, the available thiamine bioassays in the US (plasma thiamine or whole blood thiamine diphosphate (ThDP)) have reference ranges that are based on thiamine status in healthy individuals and have not been validated in those with clinical diagnoses of TDDs¹. In addition, there is uncertainty in interpreting biomarker results and a lack of consensus on which biomarker is superior at distinguishing TD⁴¹. Experts suggest that whole blood ThDP normalized to RBC volume or hemoglobin concentrations should be used to ensure data from different studies are comparable¹. Measuring serum and whole blood biomarkers concurrently would be important to validate each technique in the context of clinical TD that is responsive to replenishment. Filling the knowledge gap of clear case definitions of TDDs in non-alcohol using Veterans is an important step in achieving better outcomes with diagnosis and treatment.

Acute and chronic forms of inflammation may increase the risk of developing TD. It is accepted that inflammation is a significant risk factor for developing malnutrition^{42,43}. Acute and chronic forms of inflammation are thought to contribute to the development of malnutrition through associated anorexia. Decreased caloric intake in combination with elevated resting energy expenditure (which increases the need for thiamine as a metabolic co-factor) leads to a downward spiral of depleting thiamine stores in the face of reduced oral intake. Concomitant measurement of inflammatory markers and thiamine biomarkers combined with clinical evaluation of TDDs is an open question, the answer to which is needed to further our understanding of this condition in Veterans and to develop potential mitigation strategies.

Study Aims/Objectives:

The **objective** of this proposal is to measure the prevalence of TD and TDDs in Veterans who don't use excessive alcohol and are ill enough to require hospitalization. Additionally, we will correlate biomarkers of thiamine with signs and symptoms of TDDs which improve with thiamine replenishment. Our central hypotheses are that the prevalence of TD in this population is as high as 25% based on reports of TD in various chronic disease states^{3,12,14,19–21,24–26}, and that TDDs reversible by replenishment may occur in the “low normal” range of blood thiamine levels^{14,44}. The rationale underlying this proposal is that failing to define the prevalence of TD in this population will perpetuate the current state of underdiagnosing and undertreating TDDs which contributes to loss of independence and function. If our hypothesis is correct that the prevalence is as high as 25%, filling this knowledge gap will increase awareness of and bring action to address these problems through practice change and improved health outcomes. A parallel problem faced is that there are currently no commonly accepted clinically relevant cut-points for TD biomarkers available in the US. Clarifying the “abnormally low” biomarker cutoff levels by comparing TDDs with measured blood thiamine levels will fill a knowledge gap that has been identified¹. Through carefully defining TDDs we will fill a critical knowledge gap and assist hospitalist and rehabilitation practitioners in making the diagnosis and implementing a treatment plan. Our **long-term goal** is to increase recognition and treatment of TDDs in Veterans by describing the clinical syndromes in non-alcoholics, as well as understand the root causes of TDDs. This will improve long-term health outcomes for Veterans with acute and chronic illnesses and help them maintain independence and function. We will test our central hypothesis and attain our objectives via the following **specific aims**:

Aim 1: Utilizing a prospective cohort study design, determine the prevalence of TD, as defined by whole blood and plasma thiamine levels and symptom responsive disease, and describe social and medical factors predisposing to TD in consecutively hospitalized non-alcoholic medicine patients.

Hypothesis 1: The prevalence of TD in hospitalized Veterans who do not use excessive alcohol is between 10 and 25%, much higher than the general population estimate of less than 3%.

Aim 2: Through an open label treatment study, we will define thiamine deficiency disorders (TDDs) as cases with low or “low normal” thiamine levels and symptoms of TD that improve with thiamine replenishment. Hypothesis 2: The current bioassays of thiamine do not accurately define TDDs and individuals with results the “low normal” range will show symptom improvement with thiamine replacement.

Aim 3: Utilizing a nested case control study design, determine if acute and chronic inflammatory conditions with elevated biomarkers of inflammation increase the risk of developing TDDs. Hypothesis 3: Acute and chronic forms of inflammation cause oxidative stress which increase basal requirements for thiamine as a metabolic cofactor and increase the risk of developing TDDs.

Study Population:

We anticipate 300 patients will be enrolled in this study with an age range of 18 and older. There will be no exclusions due to gender, race, age, or ethnicity. We will endeavor to include women and minorities to the extent possible based on the inpatient population which historically has been predominantly male (95%) and white (90%). All subjects recruited for this study will be Veterans admitted to inpatient units at VA Sierra Nevada Healthcare System hospital (single site recruitment). There will be no minor children participating. The health status will be compromised from mild to severe due to the nature of being hospitalized. We will not include adults unable to consent (those who are cognitively impaired with Impaired Decision-Making Capacity). We will not enroll pregnant women as we do not admit them to the VA hospital due to lack of maternity services.

Inclusion criteria:

- anyone age 18 or older requiring full hospital admission to the medical service.

Exclusion criteria:

- excess alcohol intake as defined by the National Institute of Alcohol Abuse and Alcoholism as more than 14 standard drinks per week for men less than age 65, or more than 7 drinks per week for women or men 65 years of age or older
- unable to consent due to impaired decision making capacity.
- veterans who live more than 75 miles from the study site as that would likely hinder their ability to attend follow up visit 3.
- Veterans who suffer from quadriplegia because they cannot participate in the physical assessments
- Veterans taking thiamine supplements

Vulnerable Populations:

The population enrolled may include vulnerable populations such as those with memory loss or neuropsychiatric symptoms that may be a result of thiamine deficiency. Through this research we hope to find potential treatments for these conditions which are disabling. We will assess their decision-making capacity during the consent process utilizing the U-ARE Protocol⁴⁵.

Sample Size:

Current best estimates for TD in similar populations are approximately 25%^{19,24,27}. Such an enrollment would provide us with a precision of TDD prevalence of +/- 5.4%. A sample size of 300 and estimated drop out of 15% leaving 255 subjects would provide us with 81% power to detect an 8% absolute difference from this expected prevalence.

Recruitment Process:

We will apply for a HIPAA waiver to preliminarily review charts of newly admitted Veterans for eligibility. Each workday, we will obtain a list of veterans newly admitted to the hospital from administration since the previous workday (on the first workday of a week, this will include weekend admissions). We will not use advertising to recruit potential participants. For those who do not have exclusion criteria, we will approach the patient to discuss the study and determine if they have capacity to consent to the study. If they lack capacity at the time we approach them, we will discuss with the treatment team whether the lack of capacity is expected to be temporary, due to their acute medical condition, or permanent due to underlying neuropsychiatric disease. If it is deemed temporary, we will approach the patient later in the hospital stay when their acute conditions have

been treated and discuss the study again to see if their capacity has improved to a degree where informed consent is possible.

Screening Procedures:

The research coordinator will preliminarily review charts for exclusion criteria.

Informed Consent Process:

To obtain consent the research coordinator will approach the Veteran in their hospital room and ask if they wish to hear about the research we are conducting. If they are willing, they will describe, in plain English, the health effects of thiamine deficiency and the current knowledge deficit of what percentage of hospitalized Veterans suffer from it. We will confirm capacity utilizing the format of the U-ARE protocol⁴⁵. We will emphasize that participation is wholly voluntary and that they may stop participating at any time without penalty. We will discuss the fact that this research is designed to measure how often hospitalized Veterans suffer from thiamine deficiency which may result in the improvement of diagnosis and treatment of this condition in the Veteran population. We will describe the study procedures which will include several interviews by study staff, extra blood work which will be timed to coincide with routine blood work where possible, targeted physical examination, possible prescription of thiamine replacement. Lastly there may be a single follow up visit after treatment which will include interview, physical exam, and repeat blood draw. The total duration of participation will be four weeks or less. We will describe the fact that Veterans whom we suspect have TD based on their symptoms and/or physical exam will be prescribed oral thiamine replenishment and followed for symptom improvement. There will be no blinding of participants so that if thiamine is prescribed, they can be assured they are provided the vitamin and not a placebo. We will describe the possible risks of bleeding or bruising from phlebotomy. We will discuss the potential outcomes if the deficiency is left untreated such as worsening memory, weakness, falling, difficulties with eyesight, heart failure, nerve damage and in extreme cases death. There are no alternative treatments for TD besides vitamin replacement. If during participation in the study, we discover other vitamin or nutritional deficiencies, we will notify the patient's primary care provider to address these deficiencies. There will be no genetic material collected or stored because of this study. The consent form will also provide all participants with the principal investigator's and study coordinator's contact information to answer any questions that arise later.

Data Collection Procedures:

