10 STUDY INTERVENTIONS

Table 3: Study procedure schedule of evaluations

	Visit 1- early hospitalization	Visit 2 – late hospitalization	Visit 3 – after 2 weeks of thiamine repletion
Chart review for social and medical histories	X		
Symptom and function survey		X	X
Targeted physical exam		X	X
Nutritional history		X	
Lab draw for thiamine biomarkers	X		X
Blood draw for prealbumin , others as needed	X		
Thiamine repletion	X ¹	X ²	

1. For select patients with WE or severe symptoms of thiamine deficiency 2. all others

10.1 Visit 1 – initial hospital encounter: The Veteran's chart will be reviewed for acute and chronic medical problems, habits, and social history. We will schedule lab testing (as described below) to coincide with routine morning blood draw to avoid additional phlebotomy. For those who present with symptoms of Wernicke's encephalopathy (WE) which requires urgent parenteral thiamine replacement, we will perform our history and exam promptly and advise the primary inpatient treatment team to initiate therapy if they meet the Caine criteria⁴⁶ for WE. For all others who do not have evidence of WE, we will proceed to visit 2.

Thiamine biomarker and other micronutrient assessment: Fasting plasma thiamine levels and whole blood ThDP will be ordered for collection by lab personnel as soon as feasible after consent is obtained from the Veteran. We will also order blood levels of vitamins B12, D, and folic acid as well as prealbumin if not done via routine care within the preceding four weeks. In addition, we will extract albumin, complete blood count, and magnesium as ordered by the primary team as part of routine care. There will be no genomic sequencing, in whole or in part, as part of this analysis. Blood specimen will be collected as part of routine medical care by laboratory personnel. Lab tests not routinely run in our local laboratory will be sent out to reference labs per the usual practice of the Department of Pathology. There will be no direct handling of blood specimen by the research team. Results of the lab tests will be available in a participant's electronic medical record and will be extracted by the study coordinator and stored in a de-identified database. If they have been prescribed thiamine replenishment and the thiamine lab values are lost, we will include the remaining data gathered in the study.

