Measurements: The **primary outcome** of this study is to measure the prevalence of TD as defined by abnormally low or low normal thiamine biomarkers combined with symptoms that respond to thiamine replenishment. **Secondary outcomes** will include describing demographic, clinical, and nutritional characteristics among those with and without TDDs. A TDD will be defined as an acute condition with symptoms that are known to be due to TD and that improve with adequate thiamine replenishment.

Statistical analysis/power calculations: Our primary endpoint is the prevalence of TDDs which we will compute as the proportion of TDD cases over the total number of subjects enrolled. Given the feasibility of this study and our patient population, we believe we can enroll and follow 300 subjects over a one-year enrollment period with an anticipated drop-out rate of 15%. Current best estimates for TD in similar populations are approximately 25%^{19,24,27}. Such an enrollment would provide us with a precision of TDD prevalence of +/- 5.4%. A sample size of 300 and estimated drop out of 15% leaving 255 subjects would provide us with 81% power to detect an 8% absolute difference from this expected prevalence. To explore differences in demographic, clinical, and nutritional characteristics among those with and without TDDs, continuous variables will be compared by T-test unless parametric assumptions are not met in which case a Kruskall-Wallis test will be used. Categorical variables will be evaluated through Chi-square or Fishers exact test depending on assumptions being met. We will estimate prevalence rate ratios for association factors. If the prevalence is achieved, we estimate that we would have adequate numbers to identify a range of different rates of exposure variables among TDD and non-TDD patients. For example, with 63 TDD and 192 non-TDD patients and a 10% rate of a given explanatory variable, we would have 80% power to detect prevalence rate ratios of ~2.5 and higher in bivariate analyses.

15.2 Open label treatment study to develop standardized case definitions of treatment responsive TDDs and correlate with thiamine biomarker levels to determine clinically relevant cut-points of those biomarkers.

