Measurements: The **primary outcome** of this arm is to describe the prevalence of treatment responsive TDD symptoms in the hospitalized Veteran population. The **secondary outcome** is to explore cut-points of thiamine biomarkers that can be utilized to diagnose TDDs with more sensitivity than current clinical laboratory limits.

Statistical analysis: Descriptive features of treatment responsive TDD patients will include frequencies of symptoms, physical exam findings, and functional disability compared to patients without TDDs. We will describe each case's initial signs and symptoms and improvements. To better define the thiamine levels that differentiate thiamine responsive from thiamine non-responsive symptoms, the levels of thiamine will be compared between groups using Kruskal-Wallis test corrected for multiple comparisons. For the two thiamine biomarkers, the optimal cut-point to distinguish between thiamine responsive and thiamine non-responsive symptoms will be determined by applying the Liu method⁴⁷ to maximize the product of the sensitivity and specificity. Based on the cut-points, thiamine levels will be dichotomized into lower and higher or equal to the cut-point and the area under the receiver-operating curve (AUC), the sensitivity, specificity, positive and negative predictive values, and the likelihood ratio will be computed. These cut-points will be compared to that of the current laboratory reported abnormal cut-points. For this aim the power to identify discriminating cut-points will be dependent up on the prevalence of the treatment responsive disorder and the distribution of thiamine levels. Under conservative assumptions (alpha 0.05, beta 0.80) and a 2 to 1 ratio of negative responders to positive responders at a given thiamine cut-point level, we would need 19 responders and 38 non-responders for a given symptom to estimate an area under the curve (AUC) of 0.725 compared to a null AUC of 0.50. While there is no information to inform the reasonableness of these parameters, we believe we will have reasonable ability to explore thiamine level cut-points for treatment responsive TDD for this exploratory aim.

4.3 Nested case-control study to determine if inflammation is associated with the presence of TD in hospitalized veterans.

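### No planned analysis of whole-blood ThDP uses haemoglobin, so the 15.2 cut-point may not be comparable across studies and the 4.3 deficiency group may include anaemic but thiamine-replete patients

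*Combined protocol and SAP*

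**What the plan says.** The Background paragraph on bioassays reports: "Experts suggest that whole blood ThDP normalized to RBC volume or hemoglobin concentrations should be used". This is a cited expert suggestion, and comparability between studies is the only reason given.

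Section 10.1 then states: "Fasting plasma thiamine levels and whole blood ThDP will be ordered for collection by lab personnel". No normalised quantity is named. On the blood count it says "we will extract albumin, complete blood count, and magnesium as ordered by the primary team as part of routine care". The count is therefore extracted, but it is neither ordered by the study nor timed to the ThDP draw.

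Haemoglobin and red-cell volume do not appear in the analysis sections:

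- **15.1** defines the primary outcome by "abnormally low or low normal thiamine biomarkers combined with symptoms that respond to thiamine replenishment".
- **15.2** covers both markers: "For the two thiamine biomarkers, the optimal cut-point to distinguish between thiamine responsive and thiamine non-responsive symptoms" is found by the Liu method, and the result is compared with the limits that the laboratory reports.
- **4.3** counts a patient as thiamine deficient on either treatment response or an abnormal level by clinical laboratory standards. An abnormal level alone is enough.

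Anaemia is not an exclusion criterion, a covariate or the subject of a sensitivity analysis.

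**The concern.** ThDP measured in whole blood should reflect both the thiamine in each red cell and the quantity of red cells. The protocol does not make this argument; it is our inference from the nature of the measure. If it holds, two analyses are exposed in a population of medical inpatients.

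- **15.2.** The aim is a clinically usable ThDP cut-point, because the protocol says none is commonly accepted in the US. A cut-point on un-normalised ThDP would depend partly on the haemoglobin distribution of this one hospital's patients. It would also miss the comparability that the Background gives as the reason to normalise.
- **4.3.** Because a low level alone makes a case, a patient with normal red-cell thiamine and low haemoglobin can be counted as deficient. If anaemia accompanies chronic inflammation, part of any association between inflammation and deficiency could come from anaemia.

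**Working it through.** **1. The plan's own figure.** Section 15.2 gives 19 responders and 38 non-responders for an AUC of 0.725 against 0.50, alpha 0.05 and 80% power (written there as beta). With the Hanley–McNeil variance,

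Var(A) = [A(1−A) + (n₁−1)(Q₁−A²) + (n₀−1)(Q₂−A²)] / (n₁n₀), where Q₁ = A/(2−A) and Q₂ = 2A²/(1+A),

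the standard error at 19/38 is 0.0818 at A = 0.50 and 0.0751 at A = 0.725. Two-sided power = Φ[(0.225 − 1.96 × 0.0818)/0.0751] = Φ(0.86) = 80.5%. At 18/36 it is 78.2%, so 19/38 is the smallest 2:1 sample. The figure reproduces; the issue is an omitted step, not arithmetic.

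**2. How often anaemia could pass for a low ThDP.** Assumptions, none of them from the documents:

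- Raw ThDP = (ThDP per gram of haemoglobin) × haemoglobin.
- ThDP per gram is log-normal with log-SD s = 0.20 to 0.30.
- The laboratory's lower limit is the 2.5th percentile at a single reference haemoglobin. If haemoglobin varied in the reference population, the limit would sit lower and the rates below would be smaller.

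For a patient with normal ThDP per gram whose haemoglobin is a fraction h below reference,

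P(falsely low) = Φ(−1.96 − ln(1−h)/s).

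| Haemoglobin below reference | s = 0.20 | s = 0.25 | s = 0.30 |
|---|---|---|---|
| 0% | 2.5% | 2.5% | 2.5% |
| 10% | 7.6% | 6.2% | 5.4% |
| 15% | 12.6% | 9.5% | 7.8% |
| 25% | 30.1% | 20.9% | 15.8% |

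Example: h = 0.15, s = 0.25 gives Φ(−1.96 + 0.1625/0.25) = Φ(−1.31) = 9.5%.

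**3. Does omitting haemoglobin lower the AUC?** Suppose 0.725 is the AUC of normalised ThDP and haemoglobin is unrelated to response. The standardised separation is d = √2 × Φ⁻¹(0.725) = 0.845. Haemoglobin with log-SD c reduces the AUC to Φ[d·s/(√2·√(s²+c²))]. With s = 0.25:

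- c = 0.10: AUC 0.711, power 74.5% at 19/38.
- c = 0.20: AUC 0.680, power 59.7%.

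Now let responders have mean log-haemoglobin lower by δ. The loss vanishes when (d·s + δ)/√(s²+c²) = d, that is, δ = d(√(s²+c²) − s). With s = 0.25 this gives δ = 0.016 at c = 0.10 and 0.059 at c = 0.20, or haemoglobin about 2% to 6% lower in responders. A larger gap would make raw ThDP look the better discriminator, though for a confounded reason. The direction of the AUC change is therefore not established.

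**The case against.** - **The Background reports a suggestion, for cross-study comparability, in what is a single-site study.** This is correct. The protocol does not say that raw ThDP is invalid within a study. But a cut-point offered for wider use is where comparability matters, and the protocol cites the suggestion without giving a reason to depart from it.
- **The plan is silent on the unit; it does not commit to raw values.** This also stands. The comparators it names are laboratory limits, however, and silence leaves the choice open until results are seen.
- **A reader might infer that anaemic patients inflate the primary prevalence at the rates in the table.** The documents do not support this. Section 15.1 also requires symptoms that respond to thiamine, and plasma thiamine is a second marker. Response is judged open-label in two broad categories, so it is an imperfect filter, but the false-low rates are not prevalence errors.
- **A reader might infer that 15.2 loses power.** This is not supported either. Section 15.2 does not say that 0.725 refers to normalised ThDP, and the loss disappears if responders have slightly lower haemoglobin. The section also calls the aim exploratory and admits that nothing informs its parameters.
- **Normalised ThDP cannot simply replace raw ThDP in 4.3.** This is correct: 4.3 classifies by clinical laboratory standards, and a normalised value would have no laboratory reference limit.
- **The blood count is not guaranteed.** It exists only as ordered in routine care, with no rule for timing or missing values, so the fix has to supply one.

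**Conclusion.** The omission is real: the plan cites normalisation and extracts a routine blood count, but never uses haemoglobin. It matters most for the comparability of the 15.2 ThDP cut-point and for the 4.3 group, where an abnormal level alone counts. It matters less for the 15.1 prevalence.

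The size is conditional. For haemoglobin 10%, 15% or 25% below reference, a thiamine-replete patient would have a falsely low ThDP with probability 5–8%, 8–13% or 16–30%, against 2.5% nominal. This rests on proportionality to haemoglobin, an assumed log-SD of 0.20 to 0.30 and a 2.5th-percentile limit. Nothing in the documents says how many patients will be anaemic, so these rates cannot be turned into a number of misclassified participants. This is a worthwhile, inexpensive improvement to mainly exploratory analyses, not an error that undermines the primary endpoint.

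**What to change.** **Section 15.2.** Run the group comparison, the Liu cut-point and the AUC on ThDP per gram of haemoglobin. Take the blood count nearest the Visit 1 ThDP draw, within a stated window, and state a rule for missing counts. Report raw ThDP alongside, because the comparison with laboratory limits needs the laboratory's own unit.

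**Sections 15.1 and 4.3.** Keep the laboratory limit on raw ThDP. Add a sensitivity analysis that excludes cases who are low or low-normal on raw ThDP only and have low haemoglobin, with low haemoglobin defined in advance. In 4.3, also adjust for haemoglobin.

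**Cost.** Analysis-plan wording and one derived variable; no extra blood. Some counts may be missing or not drawn with the ThDP sample, and the normalised values have no laboratory reference limit to be judged against.
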